#### 4. UCIMC Supplementary Clinical Services

If a UCIMC clinical unit/department (e.g., phlebotomy for blood draws, pharmacy for dispensing study drug(s), radiation services for X-rays, MRIs, CT scans, and Neurology for lumbar punctures) will perform research-related procedures:

1. List the research procedure (e.g. lumbar puncture, MRI, CT Scan), and
2. Identify the unit/department that will perform the procedure.

Not applicable: This study does not involve the services of a UCIMC clinical unit/department.

#### 3. Privacy

Privacy is about the subject's ability to control how much others see, touch, or collect information about the subject. Indicate all of the following methods that will be used to assure subject privacy. *Violations of privacy include accessing a subject's private information without consent, asking personal sensitive information in a public setting, being audio recorded or photographed without consent.*

Research procedures (including recruitment) are conducted in a private room.  
 Use of drapes or other barriers for subjects who are required to disrobe.  
 Only sensitive information directly related to the research is collected about subjects.  
 When information is collected from internet sources, the internet site's privacy statement will be reviewed and followed.

*Provide a copy of the Data Use Policy to the IRB.*

Other (specify): <Type here>

#### 4. Use of Existing Biological Specimens and/or Existing Information/Data

For studies that involve use of existing (i.e. on the shelf; currently available) specimens:

1. Indicate the source of the specimens and whether the specimens were originally collected for research purposes.
2. Explain how the existing specimens will be obtained.

Not applicable: This study does not involve use of existing biological specimens.

**Source: Indicate all that apply:**

UCI/UCIMC

Originally collected for research purposes:  YES; UCI IRB number (i.e. HS#): <Type here>

NO; explain: <Type here>

UCIMC Pathology Biorepository will provide specimens.

Non-UCI Entity; specify: <Type here>

Originally collected for research purposes:  YES

*Submit a copy of the IRB Approval Notice and Consent Form for the original collection.*

NO; explain: <Type here>

Other; explain: <Type here>

For studies that involve use of existing (i.e. on the shelf; currently available) clinical data:

1. Specify the source of the clinical data.
2. Explain how the study team will access the clinical data. *Access to UCI Medical Center medical records for research purposes outside the capacity of the Honest Broker Services, such as access to physician notes, must be obtained from the Health Information Management Services.*

*For investigator initiated/authored studies only, submit a data abstraction sheet that includes a complete list of data elements/information that will be collected from (existing) records or submit the case report form (CRF; eCRF).*

Not applicable: This study does not involve use of existing clinical data. *Skip to Section 6.G.*

**Source: Indicate all that apply:**

UCI/UCIMC.

non-UCI Entity; specify: <Type here>

**How Obtained: Indicate all that apply:**

The study team will request specific patient information/data from UCIMC Health Information Management Services.

The study team will review their patients' records and abstract data directly from those records.

The study team will request specific patient information/data from UCI Health Honest Broker Services. Describe the following:

Cohort selection criteria (e.g., use the available Clinical Terms from the Cohort Discovery Tool such as Demographics: Gender, Diagnoses: Asthma, Procedures: Operations on digestive system): <Type here>

Expected cohort size/patient count: <Type here>

Cohort attributes or data elements (e.g., lab test values, medication, etc.): <Type here>

Other; explain: <Type here>

For studies that involve use of existing (i.e. on the shelf; currently available) clinical data, specify the time frame of the clinical data to be accessed (e.g. records from January 2002 to initial IRB approval).

#### 4. Collection of Photographs, or Audio/Video Recording

Describe all procedures involving the use and/or collection of photographs, or audio/video recording.

Not applicable: This study does not involve photographs or audio/video recording. *Skip to Section 6.H.*

Once the essential information has been provided to the subject and the investigator is assured that an individual candidate understands the implications of participating in this study, the subject will be asked to give consent to participate in the study by signing an informed consent form.

Specify if photographs or audio/video recording will include subject identifiable information (e.g., name, facial image). If so, indicate which identifiers will be collected.

Subject will be asked to give consent to participate in the study by signing an informed consent form and photography release form. Patient identifying information such as name and, if needed, facial image will be collected only for the purposes of their patient records, however, when evaluating photographs for the study, their name will not be released or utilized, and their identifying facial information (eyes) will be hidden. Most photographs will not be subject identifiable.

Explain whether the photographs or audio/video recording will be included in subsequent presentations and/or publications and, if so, whether subject identifiers will be included.

Publications and/or presentations that result from this study will not include subject identifiable information.

#### 4. Sharing Results with Subjects

Describe whether individual results (results of investigational diagnostic tests, genetic tests, or incidental findings) will be shared with subject or others (e.g., the subject's primary care physician). *Only tests ordered by a physician and conducted in a CLIA certified lab may be shared.*

Explain what information will be shared and how the results will be shared.

Not applicable: Individual results will not be shared with subjects. Subjects are permitted to see their own photographs.

Describe whether overall study results will be shared with subjects. Explain how results will be shared.

Not applicable: Final study results will not be shared with subjects. Subjects are permitted to see their own results.

#### 5. Statistical Considerations *(This section is required for Investigator-Authored Research)*

1. Statistical Analysis Plan: Describe the statistical method(s) for the stated specific aims and hypotheses. *Your analysis plans should match the stated study specific aims and hypotheses in Section 1.*

##### Statistical Analysis Plan

Primary Objective: The outcome of degree of improvement will be compared between those previous patients that were treated conventionally as a prospective control and those prospective patients who will be treated with assistance from the OCT device. We will use a two-sample t-test to examine the difference in degree of improvement between the two groups at each treatment.

Secondary Objective: We will present the mean/standard deviation and 95% confidence interval of all secondary outcomes (including lesion thickness, size, size of blood vessels, and density of blood vessels, and number of superficial blood vessels.) at each treatment.

2. Describe the primary statistical method(s) that will be used to analyze the primary outcome(s) or endpoints.

N/A

3. Describe the secondary statistical method(s) that will be used to analyze the secondary outcome(s) or endpoints.

N/A

4. If appropriate describe secondary or post hoc analyses of primary outcome(s) or other exploratory analysis.

N/A

5. Sample Size Determination: Explain how the overall target sample size was determined (e.g., power analysis; precision estimation), providing justification of the effect size for the primary outcome based on preliminary data, current knowledge/literature and/or cost consideration; if appropriate, provide sample size justification for secondary outcomes. Power analysis should (at least) match the primary outcome/endpoint.

Literature indicated that laser treatment of skin lesions yields varying degree of clearance across different types of lesions. For example, the Ashinoff et al. 1991 study showed 50% lesion clearance after 3 laser treatments for port wine birthmarks in 12 infants. Another Ashinoff et al. 1991 study showed 70% lesion clearance after 3 laser treatments for capillary hemangiomas in 10 infants. The Clark et al. 2002 study showed 50% lesion clearance after 3 laser treatments for rosacea in 12 adults. Last but not least, the Geronemus 1991 study showed 90% lesion clearance after 1 laser treatment for spider telangiectases in 12 adults. Based on these data, we calculated a mean of 65% ( $\pm 20\%$ ) lesion clearance after 3 laser treatments for any lesion type. Adjusting for the unique characteristics of our patient population at UCI, we estimated a mean lesion clearance of 40% ( $\pm 20\%$ ) after 1 laser treatment for any lesion type.

The two studies of laser treatment with OCT imaging assistance, Weibel et al. 2016 and Weibel et al. 2018, demonstrated that the depth of lesions and the size and density of the surrounding blood vessels varied widely across patients with burn and traumatic scars and vascular hemangiomas, and that some lesions appearing to be superficial had a much deeper component than could be visualized or palpated. Based on this insight, we hypothesized that laser treatment with imaging assistance would enable dermatologists to calibrate the laser parameters precisely to the actual depth of a lesion and the actual size and density of the surrounding blood vessels; as a result, at least 60% ( $\pm 20\%$ ) of the lesion of any type would be cleared after one laser treatment with imaging assistance as compared to 40% ( $\pm 20\%$ ) without imaging assistance.

A sample size of 34 patients, including 17 patients prospectively treated with laser and imaging assistance for lesions of any type and 17 prospective controls who received laser treatment without imaging assistance, would yield 80% power to test the aforementioned hypothesis using a two-sided two-sample t test at 5% significance level.

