### **2. Study Design**

Include an explanation of the study design (e.g., randomized placebo-controlled, cross-over, cross-sectional, longitudinal, etc.) and, if appropriate, describe stratification/ randomization/blinding scheme.

This is a longitudinal study with matched prospective controls. The patients will undergo treatment and follow-up over the course of 1-7 months. Their results will be compared to that of matched prospective controls with similar treatment and follow duration. There is no placebo, and patients will not be blinded.

Patients will be stratified based on their lesion type and the size of the lesion as these factors may impact the response to laser treatment and thus the data measurements from OCT. Photographs of the patients' treated lesions will be rated for lesion improvement by blinded physicians. OCT measurements of the lesion of interest will be used to validate the improvement and cosmetic results.

Provide precise definitions of the study endpoints and criteria for evaluation; if the primary outcomes are derived from several measurements (i.e., composite variables) or if endpoints are based composite variables, then describe precisely how the composite variables are derived.

Primary endpoints include photographic improvement of the lesion(s) of interest after 1 or more laser treatments. Two board certified dermatologists grade the degree of improvement (clearance of the lesion) in quartiles (no clearance=0-25, mild clearance=26-50, good clearance=51-75, excellent clearance=76-95, complete clearance=96-100). It will be up to the experienced treating dermatologist to determine the number of treatments necessary for maximum clearance of the lesion(s).

Secondary endpoints include measurements with OCT, which show reduced lesion thickness, lesion size, size of blood vessels, and density of blood vessels, and number of superficial blood vessels.

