### 3. Research Procedures

Provide a detailed chronological description of all research procedures.

A screening log of all potential subjects will be kept at our site. All screening evaluations must be reviewed by the investigator to establish patient eligibility prior to registering the patient for this study.

The following screening evaluation should be completed for all subjects on the first visit:

- Informed consent and photograph release form
- Focused medical history including diagnosis of lesion if applicable. This includes general questioning about the patient's health, well-being, allergies, and medications, and history of the skin lesion in question as identified by the patient and confirmed by the physician.
- Focused skin exam. This includes a detailed medical examination of the skin lesion in question.
- Documentation of area of skin to be studied. This will be determined by the patient's indication and confirmed by the physician.

On visit number one of the study, patients will consent to the study, and an area of skin to be studied will be photographed by digital photography. If the study area is on the face, subjects will be offered to protect their identity.

Non-invasive imaging will then be performed with OCT. Each individual scan with OCT takes about 30 seconds to complete, and we may perform multiple scans on larger lesions. Based on the data and information obtained, the appropriate laser device and settings will be applied for the most optimal treatment to achieve the best results with the fewest side effects. Then laser treatment will be performed on the lesion of interest. Immediate post-treatment imaging and photography will be conducted to assess the results of the treatment. This first visit should take no more than 1.5 hours: approximately 20 minutes for a medical history and focused skin examination, 30 minutes for imaging including photographs, and 30 minutes for laser treatment. These times are all maximums and will likely be shorter. The patient may take as long as needed to consent and is permitted to take the consent form home and return another day to sign and enroll.

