Some subjects may be asked to participate in more than one imaging session. They will have the option of refusing participation in additional sessions. Follow-up examinations will be performed every 4 weeks. During these examinations, photography and imaging of the lesion of interest will be performed with optional laser treatments to be performed at the discretion of the treating physician and the patient. If no laser treatment is necessary, then the visit should take no more than 30 minutes for a quick follow-up and imaging. Additional laser treatment will require no more than 30 minutes to complete. The number of follow-ups is also determined at the discretion of the treating physician and the patient but could range from 1 to 6 depending on the response of the lesion to treatment.

Matched prospective controls will be gathered to be compared against the imaged, treated, experimental group. The prospective controls will be matched to age, gender, skin type, and type of skin lesion. They will be gathered via a retrospective chart review by abstracting and data directly from our own records.

Describe the duration of a subject's participation in the study. If there are sub-studies, include duration of participation in each sub-study.

For each visit: history and skin examination-30 minutes, imaging – up to 30 mins, and laser treatment – up to 30 mins. These are all maximums and will likely be shorter.

At a follow-up, the patient may or may not receive a laser treatment thus shortening the visit. A patient would be expected to have 1-6 follow ups depending on their response to treatment, so their maximum time in this study could range from about 1 to 6 months. Each follow-up visit is made about 4 weeks from the prior visit.

List data collection instruments (e.g., measures, questionnaires, interview questions, observational tool, etc.).

*Investigator-authored, non-standardized, or un-validated measures must be submitted for review.*

Standardized photography,  
OCT

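### The primary outcome is t-tested after every treatment without adjustment, while the sample size covers one 5% test after the first treatment that nothing designates as primary

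*Combined protocol and SAP*

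**What the plan says.** All references are to the combined protocol and SAP, Section 6 unless stated.

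- **Analysis** (5. Statistical Considerations, Statistical Analysis Plan, primary objective): "We will use a two-sample t-test to examine the difference in degree of improvement between the two groups at each treatment". No multiplicity adjustment, hierarchy or primary time point follows. Items 2 to 4 of the form, which ask for the primary, secondary and other analysis methods, are each answered as not applicable.
- **Endpoint** (2. Study Design): "Primary endpoints include photographic improvement of the lesion(s) of interest after 1 or more laser treatments". The same section leaves the number of treatments to the treating dermatologist.
- **Sample size** (5. Statistical Considerations, item 5): the hypothesis is that at least 60% of the lesion, against 40% in controls, "would be cleared after one laser treatment with imaging assistance". The test is specified "using a two-sided two-sample t test at 5% significance level", with 17 per group and 80% power. The form's instruction for this item reads: "Power analysis should (at least) match the primary outcome/endpoint".
- **Photographs** (3. Research Procedures): at visit 1, "Immediate post-treatment imaging and photography will be conducted to assess the results of the treatment". After that, "Follow-up examinations will be performed every 4 weeks", with photography each time and further laser treatment optional. There may be 1 to 6 follow-ups, depending on how the lesion responds.

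**The concern.** The study makes one formal statistical claim, a 5% test with 80% power, and it concerns clearance after one treatment. The written analysis is a series of 5% tests on the primary outcome, as many as there are treatments. The written endpoint does not choose among them.

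Three things follow.

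1. If any significant result could be reported as success, the 5% level no longer holds.
2. If the tests disagree, nothing in the endpoint or analysis text says that the first-treatment result decides.
3. Later treatment is optional and follow-up depends on response, so a test after the second or a later treatment compares selected subsets and need not estimate the effect in all patients.

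The photograph behind the first-treatment test is not fixed either. It could be the one taken immediately after the laser or the one taken about 4 weeks later.

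**Working it through.** **1. Reproduce the plan's figure.** Inputs from item 5: means 60% and 40%, ±20% read as the standard deviation in each group, two-sided 5%, 17 per group.

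- Standardised difference d = (60 − 40)/20 = 1.
- Degrees of freedom = 2 × 17 − 2 = 32.
- Noncentrality = d × √(n/2) = √8.5 = 2.92.
- Power from the noncentral t distribution = 80.7%. With 16 per group it is 78.1%, so 17 is the smallest size reaching 80%.

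The stated size is therefore correct for one two-sided test.

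**2. Count the possible tests.** Laser treatment is given at visit 1 and is optional at each of up to 6 follow-ups. A treatment at follow-up 6 has no later scheduled photograph. Treatments at visit 1 and at follow-ups 1 to 5 each do, which gives at most K = 1 + 5 = 6 tests on follow-up photographs.

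**3. Chance of at least one false positive.** For independent tests it is 1 − 0.95^K: 9.8% for K = 2, 14.3% for K = 3 and 26.5% for K = 6. Tests on the same patients are correlated, which lowers these values. The documents give no correlation, so the null case was simulated with 17 + 17 patients, equal within-patient correlation ρ, an unadjusted two-sided 5% t-test at each treatment, and 100,000 replicates:

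| Tests K | ρ = 0.9 | ρ = 0.8 | ρ = 0.7 | ρ = 0.5 |
|---|---|---|---|---|
| 1 (check) | 4.9% | 5.1% | 5.0% | 5.0% |
| 2 | 6.9% | 7.9% | 8.4% | 9.1% |
| 3 | 8.3% | 10.0% | 11.1% | 12.7% |
| 6 | 10.9% | 14.1% | 16.8% | 21.1% |

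**4. Power under the possible remedies** (d = 1, first-treatment test):

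| Remedy | Level per test | Power at 17 per group | n per group for 80% |
|---|---|---|---|
| One primary test | 0.05 | 80.7% | 17 |
| Bonferroni, 2 tests | 0.05/2 | 71.2% | 21 |
| Bonferroni, 3 tests | 0.05/3 | 65.2% | 23 |
| Bonferroni, 6 tests | 0.05/6 | 54.7% | 27 |

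If photographs are missing, the single test has 75.3% power at 15 per group and 72.1% at 14.

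**5. Selection at later treatments.** This is not quantified. The documents do not describe how treatment stops in either group, so the size and direction of any bias are unknown.

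**The case against.** The best defence is that the sample-size text gives one hypothesis with one time point, one test and one significance level, in answer to a form item about the primary outcome. On that reading the first-treatment comparison is the only confirmatory one and later tests merely repeat the method. It is the natural inference, and the fix adopts it. But it appears only as the sizing hypothesis, and the endpoint and analysis text both leave the time point open.

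It is also fair that the plan contains no rule that any significant test wins, and that the study calls itself a pilot. Both points stand. They make the inflation conditional and confine the harm to the study's one formal claim.

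The six-test figures need patients in both groups to be treated at visit 1 and at five successive follow-ups, so the two- and three-test figures deserve more weight.

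Study Design says controls will have similar treatment and follow-up duration. That may make the groups more alike at later treatments, but it does not remove selection on response, and the matching list in Research Procedures does not include duration.

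Finally, Bonferroni is not the only way to keep several tests. Testing in fixed order, starting with the first treatment and stopping at the first non-significant result, holds the overall level at 5% and leaves the first test at 80.7% power. It still puts the first-treatment test first, and its later tests still use selected patients. An end-of-course endpoint would be defensible too, but it would need its own power calculation.

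**Conclusion.** The concern holds and should be fixed. The sample-size arithmetic is right, but the analysis as written does not match the claim it supports: several unadjusted tests of the primary outcome are planned, one is powered, and the powered one is not designated.

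The mismatch is certain from the text. The error-rate figures are conditional on any significant test counting as success, on an assumed equal within-patient correlation of 0.5 to 0.9, on 2 to 6 tests, and on 17 per group contributing at each. Under those assumptions the chance of a false positive is between 7% and 21%, instead of 5%. The effect of response-dependent treatment on later comparisons can be stated only qualitatively.

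**What to change.** In Study Design and in the Statistical Analysis Plan, name one primary test: a two-sample t-test, two-sided 5%, of clearance graded by the blinded raters after the first treatment and before any second one. Then:

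- Grade it on the follow-up photograph, planned about 4 weeks later, not on the immediate post-treatment one. State the accepted time window and apply the same window to the chart-review controls.
- Include every patient with a gradable photograph in that window, and report by group how many have none. State as a limitation that, for controls, having such a photograph may depend on returning, and so on response.
- Report later treatments descriptively, with numbers remaining and no claim of significance.

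**Cost.** One or two sentences in each of the two sections, and a check of which control charts hold a dated photograph between first and second treatment. Later time points lose confirmatory status. Missing photographs would lower power as shown above, but the enrolment table in Section 3 allows up to 30 consented per group with 17 needed, which leaves room. The planned 17 per group and all treatment decisions are unchanged. Keeping every test under Bonferroni would cost more: 21, 23 or 27 per group for 2, 3 or 6 tests.

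### Lesion type and size are named as likely to affect response, yet the only group comparison is an unadjusted t-test and size is not among the control-matching factors: prespecify a model adjusted for both

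*Combined protocol and SAP*

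**What the plan says.** Section 6, Study Design, states: "Patients will be stratified based on their lesion type and the size of the lesion as these factors may impact the response". Section 6, Research Procedures, obtains the controls by retrospective chart review and sets the matching factors: "The prospective controls will be matched to age, gender, skin type, and type of skin lesion". Size is not in that list. It is also absent from the variables screened for controls in Section 3 (Screening and Determining Eligibility), which are age, type or diagnosis, location, and clearance and response.

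The Statistical Analysis Plan gives one between-group method: "We will use a two-sample t-test to examine the difference in degree of improvement between the two groups at each treatment". Secondary outcomes are only described, and the further items on primary, secondary and exploratory methods are answered as not applicable. The sample-size paragraph powers the same t-test for clearance after the first treatment.

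That paragraph also shows that clearance is expected to vary by type: "50% lesion clearance after 3 laser treatments for port wine birthmarks in 12 infants"; "70% lesion clearance after 3 laser treatments for capillary hemangiomas in 10 infants"; "50% lesion clearance after 3 laser treatments for rosacea in 12 adults"; and "90% lesion clearance after 1 laser treatment for spider telangiectases in 12 adults". The hypothesis itself is for all types together: at least 60% "of the lesion of any type would be cleared after one laser treatment with imaging assistance", against 40% without.

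**The concern.** The plan identifies two prognostic factors and announces strata for them, but the strata never reach the analysis. The consequences differ for the two factors.

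- **Type** is matched. Imbalance should be small, but an unpaired, unadjusted test leaves between-type variation in its standard error. The possible loss is precision, in a study of 34 patients.
- **Size** is not a matching factor and allocation is not random. If OCT patients tend to have smaller or larger lesions than the controls, and size predicts clearance, the difference in clearance partly reflects size. The possible loss is validity of the estimate.

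**Working it through.** **Inputs from the plan.** 17 per group, means 60 and 40, SD 20 (reading the ± as an SD), two-sided 5%. No correlation of size with clearance, no size imbalance and no share of variance due to type is given, so those are assumptions shown as ranges.

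**1. The plan's own figure.** SE = 20 × √(2/17) = 6.86. Noncentrality = 20/6.86 = 2.915 on 32 df. Power = 80.7%, so 80% reproduces. The 95% CI half-width is about 14.0 points.

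**2. Size.** Bias of the unadjusted difference = SD × r × d = 20 × r × d, where r is the correlation of size with clearance and d the size difference in SDs.
- r 0.2, d 0.25: 1 point
- r 0.3, d 0.5: 3 points
- r 0.3, d 1: 6 points
- r 0.5, d 1: 10 points

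Under no true effect, r 0.3 and matched types, simulated t-test rejection is 4–7% at d 0.5 and 10–14% at d 1. In the adjusted model (r 0.3, d 0.5, four categories, type share 26%) the mean estimate is 0.0 and rejection 4.9%.

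**3. How much variance type might explain.** For 50, 70, 50, 90 at an equal mix, the mean is 65 and the variance (225 + 25 + 225 + 625)/4 = 275. Scaling by the plan's step from 65% to 40% gives 275 × (40/65)² = 104.1, and 104.1/400 = 26%. The three 3-treatment figures alone (50, 70, 50) have variance 88.9; 88.9 × (40/65)² = 33.7, or 8%.

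Neither share is firm. The 90% figure was already after one treatment. Left unscaled beside 30.8, 43.1 and 30.8, it gives a between-type variance of about 595, more than the whole planned 400. Adding a fifth category with an unknown mean of 30 to 90 moves the scaled share between 21% and 39%. So 8% and 26% are illustrations.

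**4. Power, unadjusted against adjusted for type and size.** Five categories, size unrelated to clearance. Adjusted power is noncentral-t power averaged over simulated designs.

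| Type share of variance | Types matched | Types balanced by chance |
|---|---|---|
| 0% | 80.7% vs 78.8% | 80.7% vs 73.3% |
| 8% | 81.7% vs 82.0% | 80.7% vs 76.7% |
| 26% | 83.6% vs 89.4% | 80.7% vs 84.9% |

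With matched types at 26% the CI half-width is 14.0 unadjusted and 12.3 adjusted. The t-test's null rejection is 4.1% at 8% and 2.3% at 26%: valid but conservative. With size of no value, adjustment starts to pay when type explains about 6–7% of variance if matched, or about 14% (four categories) to 17% (five) by chance.

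**5. Cost when the covariates predict nothing.** Error df fall from 32 to 28 (four categories plus size) or 27 (five). Power is about 79% with matched types, 76% if size also differs by 0.5 SD, and 68% at 1 SD. With types balanced only by chance it is 74.9% (four) or 73.3% (five).

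**The case against.** The strongest reply has four parts.

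- **This is a self-described pilot with few patients, and a model with up to six group and covariate terms is heavy for 34.** This stands in part. With 17 matched pairs in five equally likely types, a rule merging categories of fewer than 4 patients would be triggered in about 43% of studies. Merging rosacea with telangiectasia keeps only 27% of the spread (75 of 275), about a 7% share of variance, which is near break-even. Few categories and a prespecified merging rule are therefore essential. The plan does, however, set a powered 5% hypothesis test, so the choice of test matters.
- **Precision may not improve.** This stands. A reader might infer that adjusting for type must help. At an 8% share it does not, and power falls by about 4 points if types balance only by chance.
- **The size effect is hypothetical.** The documents give no correlation, imbalance or direction, and at 0.3 and 0.5 SD the false-positive rate stays near nominal. That limits the claim to a conditional bias. The plan itself names size as a possible influence, and nothing in the matching controls it.
- **Study Design does promise stratification on size.** It does, so it would be too strong to say size is ignored. What is missing is any statement of what the strata do in control selection or analysis.

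The power figures also treat clearance as continuous with SD 20, as the plan does. They were not worked out for the five grading bands.

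**Conclusion.** The point holds as a recommended improvement. The sections on design, matching and analysis are not reconciled on lesion size, and the single unadjusted comparison is open to bias if size differs between groups and predicts clearance: 3 points at assumed values of 0.3 and 0.5 SD, 1 to 10 over the range shown. For type the gain is uncertain, from nothing material to about 5 points of power with matched types, and the cited clearances cannot settle it because they mix one and three treatments.

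Three stronger readings are not supported. The stated power is not wrong. The t-test is not invalid on account of type where the matching is carried out. Adjustment would not remove confounding in general: it reduces bias from size as measured, under a correctly specified model, and leaves other differences between OCT patients and chart-review controls untouched. Nor do the documents show that size is unavailable for controls. It is absent from the screening list, but the data abstraction sheet that the form asks for is not among the documents.

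**What to change.** 1. Make the primary comparison a prespecified linear model of clearance after the first treatment (the time point that was powered) on group, lesion-type category and baseline lesion size. Report the adjusted difference with its 95% CI, and keep the t-test as a sensitivity analysis.
2. Fix a small number of type categories before photographs are graded, with a rule for merging sparse ones. Keep apart types expected to clear differently. A single vascular group would keep none of the cited spread, because Section 1 counts all four cited types as vascular.
3. Match controls on those same categories, and say whether matching is 1:1 or by frequency.
4. Reconcile Study Design with Research Procedures on size: either match on it in broad bands or state that adjustment alone handles it.
5. Add baseline size to the control data and measure it the same way in both groups, for example from baseline photographs. OCT size will not serve, since controls have no OCT. If this is not possible, adjust for type alone and state the limitation.

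The cost is one more control variable and 4 to 5 error degrees of freedom. The price in power is small only if the type matching is carried out and size does not differ much between groups. If the covariates turn out to be uninformative, power is about 79% with matched types, 73–75% if types balance only by chance, and about 68% with matched types and a 1 SD size difference.
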